The present study includes CT and dental examinations developed by Allergan with input from consultants and specifically designed to identify potential effects of BOTOX treatment of MMH on the mandible and teeth. The CT scan captured by a CT technologist will be transferred to a central reader, who will review it to assess for changes in lower facial shape (masseter muscle volume, bigonial width, mandibular flare angle, and gonial angle) as well as relevant indicators of change in bone structure (mandibular condylar head shape, mandibular condylar cortical surface, mandibular condylar head, mandibular condylar position, glenoid fossa/eminence, and cortical thickness under the insertion point of the masseter muscle at the mandibular ramus). The dental examination will be conducted by a dentist to assess for any potential changes in dentition, occlusion, and overall oral health (Attachment 12.1.7). Both CT and dental measures will be taken at screening (considered as baseline), day 90, and at study exit (day 360 or study discontinuation).

In summary, the data obtained from this study will be used to develop a better understanding of the safety and efficacy of different dose regimens of BOTOX for the treatment of MMH.

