#### 5.4 Treatment Allocation Ratio and Stratification

Subjects will be randomly allocated to BOTOX or placebo using the automated interactive voice response system (IVRS) or the interactive web response system (IWRS).

Subjects will be stratified by baseline (day 1) MMPS grade (4 or 5).

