#### 7.3 Hypothesis and Methods of Analysis

#### 7.3.1 Primary Efficacy Analyses

Descriptive statistics for change from baseline in lower facial volume for each study visit (sample size, mean, standard deviation, median, minimum, and maximum) will be provided by treatment regimen for all scheduled visits.

The primary efficacy analysis will be based on the mITT population. Day 90 is the primary timepoint.

The following set of hypotheses will be used to compare the BOTOX groups with placebo:

- Null hypothesis: BOTOX and placebo are equally effective in changing lower facial volume at day 90.
- Alternative hypothesis: BOTOX and placebo are not equally effective in changing lower facial volume at day 90.

[figure not shown]
The change from baseline in lower facial volume at each visit will be analyzed using an ANOVA model with treatment and baseline (day 1) MMPS grade as factors. In addition, 2-sided 95% confidence intervals for the treatment differences will be provided.

[figure not shown]
Analysis will be performed for the PP population and also based on observed data (ie, strictly data that falls within the visit windows) for the mITT population.

[figure not shown]

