### **2.3.5 Handling Drop-out or Missing Data**

For efficacy analyses of mITT population of the change from baseline in lower facial volume using VECTRA 3D images, MMPS, lower facial width, mandibular facial angle, CT masseter muscle volume, LFSC, and LFSQ, last observation carried forward (LOCF) will be used to impute missing values for each scheduled visit. Only missing data for visits up to day 180 of each treatment cycle will be imputed. Missing data for visits after day 180 of each cycle will not be imputed. If a subject exited the study before day 180 of a treatment cycle, visits after the study exit will not be imputed.

Missing baseline values for lower facial width, mandibular facial angle, CT masseter muscle volume, LFSC, and LFSQ will be imputed using the average of subjects with non-missing values. Missing values for change from baseline in lower facial volume using VECTRA 3D images at day 30 will be imputed using the average of subjects with non-missing values.

For angle measurements, the average degree from both sides of the face will be determined first; if the degree of angle is missing for 1 side of the face, then the angle for the subject will be based on the angle of the other side of the face. If a subject's average is a half-degree value, it will be rounded up to an integer (eg, 30.5 degree will be rounded up to 31 degrees).

For rating an individual's MMPS score, the average of the scores from both sides of the face will be determined first; if a score is missing for 1 side of the face, then the score for the subject will be based on the score of the other side of the face. If a subject's average is a half-grade value, it will be rounded up to an integer to remain consistent with the original scale (eg, 1.50 will be rounded up to 2).

When implemented, imputation of missing values will be performed only for subjects who receive a treatment in the pertinent treatment cycle. For example, only subjects receiving the second treatment will have values imputed in treatment cycle 2; subjects who discontinued from the study during the first treatment will not have any data imputed in treatment cycle 2.

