##### **4.1 Demographics**

Demographic data will be collected at the screening visit, including age, gender, race, weight, height, and body mass index (BMI). Age, weight, height and BMI will be analyzed with descriptive statistics (sample size, mean, SD, median, Min, and Max). Age group (18-35 years versus 36-50 years), gender, and race (Asian versus non-Asian) will be analyzed with frequency (counts and percentages).

Similar analyses will be done for the Safety population.

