##### **4.2 Disease Characteristics**

For the mITT population, the distribution of the baseline MMPS will be summarized.

The distribution of the baseline lower facial width, mandibular facial angle, CT masseter muscle volume (total and defined region), investigator and subject LFSC will be summarized by treatment regimen for the mITT population.

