### **5.2 Primary Efficacy Analyses**

Descriptive statistics for change from baseline in lower facial volume for each study visit (sample size, mean, standard deviation, median, minimum, and maximum) will be provided by treatment regimen for all scheduled visits.

The primary efficacy analysis will be based on the mITT population. Day 90 is the primary timepoint.

The following set of hypotheses will be used to compare the BOTOX groups with placebo:

- Null hypothesis: BOTOX and placebo are equally effective in changing lower facial volume at day 90.
- Alternative hypothesis: BOTOX and placebo are not equally effective in changing lower facial volume at day 90.

The change from baseline in lower facial volume at each visit will be analyzed using an ANOVA model with treatment, and baseline MMPS grade as factors. In addition, 2-sided 95% confidence intervals for the treatment differences will be provided.

Analysis will also be performed based on observed data (ie, strictly data that falls within the visit windows) for the mITT population.

Among-group comparisons for the placebo groups will be analyzed using an ANOVA model with treatment as factor to test whether they are combinable. If the difference among the placebo groups are significant, sensitivity analysis will also be done for the primary variable using an ANOVA model with treatment, cohort number (as numeric variable) and baseline MMPS grade as factors.

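### The primary ANOVA is valid but adjusts for baseline severity only through MMPS grade 4 or 5; pre-specifying screening CT masseter volume as a covariate could add precision at almost no cost

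*SAP*

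**What the plan says.** SAP 5.2 has the change in lower facial volume "analyzed using an ANOVA model with treatment, and baseline MMPS grade as factors". Protocol 7.3.1 gives the same model: "analyzed using an ANOVA model with treatment and baseline (day 1) MMPS grade as factors". Protocol 7.2 and the Protocol Summary agree. MMPS grade is also the only randomisation stratum (Protocol 5.4). Inclusion criterion 4 admits grades 4 and 5 only.

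Protocol 1.3 says of CT: "Both CT and dental measures will be taken at screening (considered as baseline), day 90, and at study exit". SAP 4.2 tabulates baseline CT masseter volume in two forms, for the whole muscle and for a defined region. SAP 2.3.5 provides for missing baselines: "CT masseter muscle volume, LFSC, and LFSQ will be imputed using the average of subjects with non-missing values". Weight, height and BMI are recorded at screening (SAP 4.1), and weight is summarised as a safety variable (SAP 6.7). In the visible text none of these measures enters the primary model.

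Protocol 12.1.2 defines the outcome as the volume between two registered surfaces, one at baseline and one after treatment. The visible text describes no absolute baseline lower facial volume.

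**The concern.** For a change score, the natural covariate is the baseline value of the same measure. Here no such value is visible, so baseline information reaches the model only through a two-level grade. CT masseter volume is the nearest substitute. It is continuous, centrally read, obtained before randomisation, and measures the tissue whose shrinkage should produce the surface change. Baseline weight is a secondary candidate.

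If such a covariate predicts the change beyond MMPS grade, leaving it out makes the intervals wider than they need to be. That applies to all seven planned comparisons: four doses against placebo and three adjacent-dose pairs. The documents state no effect size for the adjacent-dose pairs. At stake is precision, not validity.

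**Working it through.** **Inputs from the documents.** 40 BOTOX and 10 placebo per cohort, effect size 1, one-sided 0.10, 93% power (Protocol 7.5). Tests at two-sided 0.05 (SAP 2.3.7). Placebo pooled over four cohorts, 4 × 10 = 40 (SAP 5). Final residual df with about 200 subjects: 200 − 5 treatment means − 1 for MMPS = 194.

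**Assumptions.** Partial correlation r between the added covariate(s) and the outcome, given MMPS grade: 0 to 0.5. Illustrative smaller effect: 0.5 SD. Full enrolment, no dropout. Two df deducted for two covariates when r > 0.

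**Step 1: the plan's own figure.** Noncentrality = 1/√(1/40 + 1/10) = 2.83. With 48 df and one-sided 0.10, power is 93.6%, which agrees with the stated 93%.

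**Step 2: effect of adjustment.** The standard error (SE) is multiplied by √(1 − r²). The equivalent sample size is multiplied by 1/(1 − r²). Noncentrality becomes d/√[(1 − r²)(1/n₁ + 1/n₂)]. Power is noncentral t, two-sided 0.05, with 48 df (46 adjusted) for 40 vs 10 and 194 df (192 adjusted) for 40 vs 40.

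| r | CI narrower by | Equivalent N | 40 vs 10, d = 1 | 40 vs 40, d = 1 | 40 vs 40, d = 0.5 |
|---|---|---|---|---|---|
| 0 (planned ANOVA) | 0% | × 1.00 | 79.1% | 99.4% | 60.5% |
| 0.2 | 2.0% | × 1.04 | 80.7% | 99.5% | 62.2% |
| 0.3 | 4.6% | × 1.10 | 82.7% | 99.7% | 64.5% |
| 0.5 | 13.4% | × 1.33 | 89.2% | 99.9% | 72.9% |

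**Step 3: the cost if the covariates predict nothing.** The SE is multiplied by about √(1 + 2/df), with df counted after adjustment. Final analysis: √(1 + 2/192) = 1.005. One cohort of 50 (47 df before, 45 after): √(1 + 2/45) = 1.022.

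**Step 4: if the covariate matters only in treated arms.** Assume a within-arm correlation of 0.5 in the four BOTOX arms, 0 in placebo, 40 per arm and unit variance.
- The common slope is 0.8 × 0.5 = 0.4.
- Residual variance is 1 − 2(0.4)(0.5) + 0.16 = 0.76 in a BOTOX arm and 1 + 0.16 = 1.16 in placebo.
- For dose against placebo the average is (0.76 + 1.16)/2 = 0.96, so the true SE falls by 1 − √0.96 = 2%.
- For adjacent doses it falls by 1 − √0.76 = 13%.
- The pooled residual variance is 0.8 × 0.76 + 0.2 × 1.16 = 0.84, so the model would report an 8% reduction for every contrast. For the placebo contrasts most of that would not be real.

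**Step 5: chance imbalance.** Between two groups of 40 randomised together, a standardised covariate differs with SD √(1/40 + 1/40) = 0.22. At r = 0.5, a two-SD imbalance moves the unadjusted difference by 0.5 × 2 × 0.22 = 0.22 outcome SD. ANCOVA removes that component.

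**The case against.** The ANOVA adjusts for the randomisation stratum, uses the actual grade when a subject was mis-stratified (SAP 2.3.4), and is the same in both documents. A reader might infer that the model is wrong or biased. It is not: it is a valid analysis of the within-cohort randomised comparison. This stands.

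No document gives a correlation, SD or R² for CT volume or weight. MMPS already grades masseter bulk by sight and palpation, and entry is restricted to two grades, so little correlation may remain. This stands, and it is why the table starts at zero. Step 4 shows a further limit for the placebo contrasts, which carry the stated hypotheses.

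A reader might infer that the trial is short of power. At the planned effect size, the final pooled comparison is not.

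A reader might also take the covariate as measured on every subject. SAP 2.3.5 foresees missing baseline CT volumes and substitutes the mean. An imputed mean keeps the subject in the model but adds no information about that subject.

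Nor would adjustment repair the sequential design. Cohorts enrol one after another, so adjacent doses are not randomised against each other, and about 30 of the 40 pooled placebo subjects come from cohorts other than that of the dose being compared. ANCOVA removes imbalance in the measured covariate, not differences in calendar time, site or rater. SAP 5.2 handles cohort differences separately, by a placebo combinability test and a conditional sensitivity model.

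Much of the SAP after the visible part of 5.3 is redacted. A supportive adjusted analysis may exist there, but the visible primary model is unadjusted for any continuous baseline.

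Finally, Protocol 7 requires the SAP to be final before the first day 90 snapshot. Replacing the primary model later could look data-driven. This limits when the change can be made and does not remove its merit.

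**Conclusion.** The point holds as an efficiency recommendation. The primary model uses one two-level severity factor and leaves out a continuous baseline measure of the target muscle that the trial already collects.

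The gain depends on an undocumented correlation. It ranges from nothing at r = 0 to intervals about 13% narrower at r = 0.5, and could be only about 2% against placebo if baseline volume predicts change only in treated arms. At effect size 1, final 40 vs 40 power is already about 99%. The useful gain is in interval width, in effects nearer 0.5 SD (60.5% to 64.5% at r = 0.3, 72.9% at r = 0.5), in adjacent-dose contrasts, and in a 40 vs 10 look at one cohort (79.1% to 82.7% or 89.2%).

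The possible loss is small: an SE about 0.5% wider in the final analysis, or about 2% wider in one cohort. That asymmetry supports the change even though r is unknown.

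**What to change.** In SAP 5.2, with matching text in Protocol 7.2 and 7.3.1 and the Protocol Summary:

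- Pre-specify an ANCOVA of change in lower facial volume with treatment, baseline MMPS grade and screening CT masseter muscle volume. State which of the two CT volumes is used. Screening weight is an optional further covariate; post-treatment weight must not be used.
- Use the mean imputation in SAP 2.3.5 for missing baseline CT volume and report how many values were imputed. If weight is added, give it a missing-value rule, since none is visible.
- Keep the planned ANOVA as a supportive analysis.
- Because of Step 4, report a heteroscedasticity-robust SE alongside the model-based one for the placebo contrasts.
- If unblinded results have already reached those who choose the analysis, leave the ANOVA as primary and add the ANCOVA as a labelled sensitivity analysis.

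Cost: no new data, one or two degrees of freedom, and a short amendment to both documents. If the primary model changes in the SAP alone, SAP 11, which now declares no deviations from Protocol Section 7, must record it.

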# 3 Study Design

This is a multicenter, randomized, placebo-controlled, up to 2-treatment, dose-escalation study to assess a range of doses of BOTOX for the treatment of MMH. Up to 16 scheduled

visits are planned: screening (day -56 to day -1), day 1 (randomization/treatment), day 14 (telephone followup), monthly (days 30, 60, 90, 120, 150, 180 [possible retreatment]), and day 194 (telephone followup, only for subjects retreated at day 180), monthly (days 210, 240, 270, 300, and 330), and study exit (day 360).

After completion of all baseline study procedures and re-verification that the subjects meet all inclusion and exclusion criteria, subjects will be randomized and enrolled in cohorts of approximately 50 subjects each. Within each cohort, subjects will be randomized 4:1 to BOTOX (N = approximately 40) or placebo (N = approximately 10). Stratification will be by baseline (day 1) MMPS grade. Approximately 70% of the enrolled population in each cohort will be Asian, and subjects of Asian race will be further grouped by self-identified ethnicity (Chinese, Japanese, Korean, or other). Each cohort will be enrolled over approximately a 2-week period. When at least 50 subjects have been enrolled, randomization will be halted to allow observation of the cohort through the day 90 visit. The next cohort will be enrolled following a planned independent Data Review Committee (DRC) meeting (see Section 3.1) and Allergan's written notification to proceed.

On day 1, subjects will receive a single treatment of either BOTOX or placebo administered bilaterally to the masseter muscles as 3 injections/masseter in the area of maximal muscle bulge. The initial BOTOX total dose will be 24 U (12 U/masseter) and the maximum total dose will be 96 U (48 U/masseter). Table 2 shows the planned dose-escalation scheme.

Table 2 Dose Escalation by Cohort

Cohort	Total Dose	Target Sample Size	Target Total Subjects/Cohort
1	24 U	40	50
1	placebo	10	
2.	48 U	40	50
2	placebo	10	
2	72 U	40	50
3	placebo	10	
4	96 U	40	50
4	placebo	10	50

Based on the DRC assessment and provisions for retreatment, subjects who meet the retreatment criteria (see Section 5.10) at the day 180 visit may receive a second study treatment. The second treatment is only allowed at the day 180 visit, and the same dose as day 1 will be administered.

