# 7.2 Collection and Derivation of Primary and Secondary Efficacy Assessments

Efficacy results for all study visits will be summarized based on time since injection. Visit windows for all timepoints will be described in the statistical analysis plan.

Pairwise comparisons will be done between each BOTOX group and the placebo group. A pairwise comparison will also be done between a BOTOX group and the next higher dose BOTOX group. For interim analyses, subjects in the placebo group(s) from previous cohort(s) will be pooled with the placebo group from the current cohort for analysis if the results for the placebo groups are combinable. For final analysis, all subjects who received placebo will be pooled together as a total placebo group if the results for the placebo groups are combinable. Details will be specified in the Analysis Plan.

The primary efficacy variable will be the lower facial volume at day 90. The change from baseline in lower facial volume will be analyzed by analysis of variance (ANOVA) with treatment and baseline (day 1) MMPS grade as factors to assess the response between groups.

For analysis of the mITT population, the last observation carried forward (LOCF) method will be used to impute missing values. For analysis of the PP population, observed data without imputation will be used.

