#### 12.1.2 Lower Facial Volume Measurement

The lower facial volume measurement (cm^3) will be performed by

[figure not shown]
To measure the difference in volume between two 3D surface models from different timepoints (ie, baseline and posttreatment), the models are first registered in 3D space such that relative surfaces unrelated to the treatment regions are correspondingly aligned. The analysis region is then defined using a series of anatomical landmarks placed on the baseline surface that are then projected mathematically to the posttreatment surface and verified by the analysis technician.

[figure not shown]
In Figure 2, the green-shaded region represents the defined measurement selection area created by the perimeter formed using landmarks (C-F-D-E). Anatomical landmarks are located at: Lateral canthus (A), Alar recess (B), Earlobe attachment point (C), Prejowl sulcus (D), Mandible point (E). A single interpolated landmark (F) is also used at the intersection point of surface lines between points (A)-(D) and (B)-(C).

The difference in volume is then measured between the select region of the baseline surface and the select region of the posttreatment surface. The lower facial volume is the summed volumes for both the left side and the right side of the face, which will be compared between each paired baseline/posttreatment timepoint for the study.

[figure not shown]
In response to treatment, the region is expected to decrease in volume.

[figure not shown]

[figure not shown]

[figure not shown]

[figure not shown]

[figure not shown]

[figure not shown]

[figure not shown]

[figure not shown]

[figure not shown]

[figure not shown]

[figure not shown]

[figure not shown]

[figure not shown]

[figure not shown]

[figure not shown]

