## **5. Efficacy Analyses**

Pairwise comparisons will be done between each BOTOX group and the placebo group. A pairwise comparison will also be done between a BOTOX group and the next higher dose BOTOX group.

All subjects who received placebo will be pooled together as placebo group for analyses.

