**11. Deviations from Protocol Section 7**

Not applicable.

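### Placebo is pooled over four sequential cohorts without condition, and the only readable cohort adjustment waits on a weak pre-test and assumes straight-line drift

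*SAP*

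**What the plan says.** Protocol 3 and its Table 2 give each dose to a single cohort of about 40 BOTOX and 10 placebo subjects. Cohorts run in sequence: "When at least 50 subjects have been enrolled, randomization will be halted to allow observation of the cohort through the day 90 visit". Further enrolment then waits for the Data Review Committee meeting and the sponsor's written go-ahead.

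For the final analysis, Protocol 7.2 states that "all subjects who received placebo will be pooled together as a total placebo group if the results for the placebo groups are combinable", and adds: "Details will be specified in the Analysis Plan".

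SAP 5 has no such condition: "All subjects who received placebo will be pooled together as placebo group for analyses". The primary ANOVA in SAP 5.2 contains treatment and baseline MMPS grade, with no cohort term. SAP 5.2 does test whether the placebo groups differ, but the consequence is limited: "If the difference among the placebo groups are significant, sensitivity analysis will also be done for the primary variable". The model then used is an "ANOVA model with treatment, cohort number (as numeric variable) and baseline MMPS grade as factors". A significant pre-test therefore adds an analysis and leaves the pooling as it was.

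SAP 11, headed "Deviations from Protocol Section 7", answers that the item does not apply. Parts of SAP 5 are redacted, so what follows concerns the readable text.

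**The concern.** For any given dose, about 30 of the 40 pooled placebo subjects were randomised in other cohorts, months apart. In the primary model the dose versus next-dose contrasts are wholly between cohorts and unadjusted. If the change in lower facial volume drifts between cohorts for reasons other than drug, the drift enters both sets of estimates.

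The planned safeguard has two limits. It runs only if a test on four groups of about 10 is significant. It then fits cohort as one slope, which removes exactly linear drift (also from next-dose contrasts) but not a step or a U-shape.

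Protocol 1 says the study should help design later studies. A dose-response pattern mixed with cohort effects, behind a check that will usually not run, is a poor basis for that.

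**Working it through.** **Inputs.** 40 BOTOX and 10 placebo per cohort, effect size 1 (Protocol 7.5); two-sided 0.05 for all tests (SAP 2.3.7). Size and shape of drift are assumptions, since the documents give none. All effects are in SD units, and the MMPS term is left out of the calculations.

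**1. The protocol's own figure.** 40 vs 10, effect size 1, one-sided 0.10: SE = √(1/40 + 1/10) = 0.354, noncentral t with 48 df, power 93.6% (stated: 93%). It reproduces. The protocol thus powered each dose against its own cohort's placebo.

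**2. Power of the pre-test.** Noncentral F, df 3 and 36, noncentrality 10·Σ(μᵢ − μ̄)². For one cohort shifted by δ this is 7.5δ².

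**3. Bias under pooling.** Own-cohort mean minus the mean over cohorts: 0.75δ for the shifted cohort's dose and −0.25δ for each other dose.

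**4. Type I error.** No drug effect, SE = √(1/40 + 1/40) = 0.224, noncentral t with 78 df.

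| Shift of one cohort | Pre-test detects | Bias, own dose | Type I, own dose | Type I, each other dose |
|---|---|---|---|---|
| 0.25 SD | 8% | 0.19 SD | 13% | 6% |
| 0.5 SD | 17% | 0.375 SD | 38% | 9% |
| 1 SD | 57% | 0.75 SD | 91% | 20% |

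For linear drift from 0 to 0.5 SD over the four cohorts, the pre-test detects 13%. Bias is −0.25, −0.08, +0.08 and +0.25 SD for doses 1 to 4, and simulated type I error is about 20% for doses 1 and 4 and 6–7% for doses 2 and 3. Over the shapes tried, 80% pre-test power needs drift of 1.10 to 1.48 SD, more than the design effect itself.

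**5. How often the gate is shut when it matters.** In 20,000 simulated trials with cohort 4 shifted by 0.5 SD, its dose was falsely significant in 38.1%, and in 32.0% this happened with a non-significant pre-test: 0.320 / 0.381 = 84%.

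**6. The numeric-cohort model when it does run.** Each dose sits in one cohort, so only placebo informs the slope. Centre cohort as x = −1.5, −0.5, 0.5, 1.5, with Σx² = 5. For a 0.5 SD shift in cohort 2, the slope is (−0.5 × 0.5)/5 = −0.05 and the placebo mean is 0.125. Fitted values are 0.20, 0.15, 0.10, 0.05, and the bias left is −0.20, **+0.35**, −0.10, −0.05 SD. The three next-dose contrasts are biased by +0.55, −0.45 and +0.05 SD, against +0.50, −0.50 and 0 unadjusted. A shift in cohort 1 leaves +0.15, −0.20, −0.05, +0.10 SD; a shift in cohort 4 mirrors this. Linear drift leaves 0. A 0.5 SD shift in both cohorts 1 and 4 leaves ±0.25 SD, the same as with no adjustment.

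**7. Cohort as a four-level class variable.** Bias is 0 for every additive shape tried, and simulated type I error is 4.7–5.2%.

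| Contrast | SE, pooled | SE, class cohort | Power, pooled | Power, class cohort |
|---|---|---|---|---|
| Dose vs placebo, effect 1 SD | 0.224 | 0.354 | 99% | 79–80% |
| Next dose, difference 0.5 SD | 0.224 | 0.50 | 60% | 17% |
| Next dose, difference 1 SD | 0.224 | 0.50 | 99% | 51% |

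The next-dose SE is √(2(1/40 + 1/10)) = 0.50. The 79–80% range reflects 48 versus 192 residual df.

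**The case against.** The strongest reply is that drift is assumed throughout. The outcome is a within-subject volume difference, "which will be compared between each paired baseline/posttreatment timepoint for the study", on registered surfaces, so stable site or imaging differences should largely cancel. This stands: the finding is exposure to bias, not evidence of it. What remains is drift in the change itself. The placebo groups do differ in one documented way: total injection volume rises from 0.6 to 2.4 mL across cohorts (Protocol Table 3).

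Second, an extra sensitivity model leaves the primary error rates untouched and is itself noisy. Both are true. The gap between pooled and own-cohort placebo means has SD √(1/10 − 1/40) = 0.274. At a 0.5 SD shift the expected gap of 0.375 SD exceeds 1.96 of these in about 28% of trials, against 17% for the pre-test. The model's value is an estimate and interval free of additive cohort drift, available in every trial.

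Third, the one-cohort shift is a severe shape, and 1 SD equals the whole design effect. The linear figures above are milder but still give about 20% at the end doses.

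Fourth, the SAP calls cohort numeric and also lists it among the factors. The explicit parenthesis favours the single-slope reading, but the wording needs correcting.

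Last, the protocol delegates details to the SAP, and redacted text might hold another analysis. Delegating details does not remove a stated condition. The redaction limits only the claim that no other cohort analysis exists.

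**Conclusion.** The concern holds. The mismatch between Protocol 7.2, SAP 5 and SAP 11 rests on the documents alone and needs no assumption about drift. The modelling weakness depends on drift that the documents do not quantify. For a one-cohort shift between 0.25 and 1 SD, the gate opens in 8% to 57% of trials, while type I error for the affected dose is 13% to 91%. When the numeric model does run, it is unbiased only for linear drift. These figures assume additive drift equal in both arms of a cohort, equal variances, the planned 40 and 10 per cohort, and no MMPS term. Type I error is two-sided, and the same drift could equally hide a real effect. The change should be made; it does not require abandoning the pooled primary analysis.

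**What to change.** In SAP 5.2:

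- Keep the pooled analysis primary. Always run the cohort-adjusted sensitivity analysis of dose versus placebo for the primary variable, whatever the pre-test shows.
- Enter cohort as a four-level class variable, so that each dose is compared with its concurrently randomised placebo under a common residual variance. Remove the numeric wording.
- Label dose versus next-dose contrasts as non-randomised comparisons across cohorts. Placebo-adjusted versions from the same model may be shown as supportive only.

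In SAP 5 and SAP 11: state what happens when the placebo groups are not combinable, and either restore the condition in Protocol 7.2 or declare the departure from it.

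Cost: one model and a few sentences, with no new data. Dose versus placebo intervals in the sensitivity model are about 58% wider (0.354/0.224 = 1.58). That is the same 40 versus 10 comparison the protocol powered. Adjusted next-dose intervals are about 124% wider (√(0.25/0.05) = 2.24), which is why they should be supportive only. The primary analysis keeps its exposure to drift, but readers would always have an estimate to set against it.
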